8.1.1 Solicited Adverse Events

Solicited AEs for this study are pre-specified in Section 8.1.1 of the protocol and include both injection site reactions (ie, pain, bruising, redness, and swelling) and systemic events (ie, oral temperature [for assessment of fever], chills, muscle pain, joint pain, diarrhea, nausea, vomiting, headache, and fatigue) that are reported within seven days following the Day 0 vaccination and are solicited by diary. These events are considered related to the test article and are collected using a severity rating of 0 (did not occur), or 1, 2, or 3 (mild, moderate or severe, respectively), using the maximal severity observed for the specific symptom post-vaccination. Notable exceptions include oral temperature, which is collected as a continuous variable and that uses temperature grade ranges established in the toxicity grading scale (TGS), and events of injection site redness and swelling, which will be measured using a Subject Measurement Tool (see protocol, Appendix 4). Oral temperature (fever) will be summarized by severity according to regulatory guidance, eg, Normal $\leq 38.0^{\circ}$ C, Mild = $38.0 - 38.4^{\circ}$ C, Moderate = $38.5 - 38.9^{\circ}$ C.

a set of concentric circles with diameters that correspond to TGS ranges that are also used to assign severity.

Injection Site (local)	Systemic Events				
Events	General Gastrointestinal		Respiratory/Facial		
Pain	Oral temperature	Nausea	Eye redness		
Bruising	Chills	Vomiting	Facial swelling		
Redness	Muscle pain	Diarrhea	Eyelid swelling		
Swelling	Joint pain		Hoarseness		
	Headache		Sore throat		
	Fatigue		Cough		
			Difficulty breathing		
			Wheezing		
			Chest tightness		
			Difficulty swallowing		

 Table 3:
 Listing of Diary Solicted Events

Solicited AEs will be tabulated and analyzed by the verbatim terms specified in the diary, and not MedDRA coded. Analysis will use exact diary wording (ie, "muscle pain" rather than changing it to "myalgia"). Only solicited adverse events which record a start date within the 7-day window of the Day 0 to Day 6 post-vaccination period will be included in the tabular summary and listing of solicited events. Solicited AEs will be presented by treatment group for all subjects.

Definitions for Systemic Definitions for Local Adverse Events Adverse Events **Severity Grade** Visual Local AE Size Non-Visual Local AE Systemic AE Grading **Grading Description Grading Description** Description No noticeable symptom or Reaction size (greatest single 0 – Normal No noticeable symptom diameter) < 2.5 cm finding Discomfort or tenderness Mild symptoms or diagnostic observations; intervention Reaction size (greatest single noticeable, but does not 1 - Milddiameter) 2.5 to 5.0 cm interfere with normal daily not indicated: no interference activities with normal activity Moderate symptoms or Moderate discomfort or diagnostic observations; Reaction size (greatest single tenderness on firm pressure; 2 – Moderate some interference with diameter) > 5.0 to 10.0 cm causes some limitation of normal activity, not requiring normal daily activities medical intervention Severe symptoms, Severe pain at rest, pain or significantly disrupts or Reaction size (greatest single tenderness immobilizes the prevents normal daily 3 – Severe diameter) > 10.0 cminjected limb and prevents activities, generally requires normal daily activities medical attention/intervention

 Table 4:
 Definition of Severity Grading for Adverse Events

Severity Grade	Gast	Foren		
	Nausea	Vomiting	Diarrhea	rever
0 - Normal	No noticeable symptom	No noticeable symptom	No noticeable symptom	< 38.0
1 – Mild	No interference with activity, or 1 to 2 episodes/ 24-hour period	No interference with activity, or 1 to 2 episodes/ 24-hour period	1 to 3 unformed (loose) stools/24-hour period	38.0 to 38.4
2 – Moderate	Some interference with activity, or > 2 episodes/ 24-hour period	Some interference with activity, or > 2 episodes/ 24-hour period	4 to 5 unformed (loose) stools/24-hour period	38.5 to 38.9
3 - Severe	Prevents daily activity, or requires intravenous hydration	Prevents daily activity, or requires intravenous hydration	≥ 6 loose stools/ 24-hour period, or requires intravenous hydration	> 38.9

 Table 5:
 Severity Grade Definition for Solicted Gastrointestinal Adverse Events and Fever

Solicited AEs, collected from the subject diary, which continue after the collection period(s) (ie, post-vaccination Day 6) will be captured by verbatim term, on an AE electronic case report form (eCRF) page and flagged in the listing of solicited AEs.

The following summaries of solicited AEs will be presented by treatment group as part of the primary analysis of safety:

- Summary of solicited treatment-emergent AEs by the verbatim terms specified in the diary and within the post-vaccination window (Days 0-6).
- A summary of all solicited AEs by severity (mild, moderate, severe), and within the post-vaccination window (Days 0-6).

8.1.2 Unsolicited Adverse Events

Unsolicited adverse events are defined as any adverse events occurring within the 7-day window following vaccination and not specifically solicited in the diary, or any solicited event that occurs outside the 7-day diary solicitation period. The number (percentage) of subjects with unsolicited AEs will be summarized by MedDRA SOC and PT.

The following summaries of unsolicited AEs will be presented for all subjects in the Safety Population as part of the primary analysis of safety:

- Overall summary of unsolicited AEs by treatment group (Days 0 21).
- A summary by severity (mild, moderate, or severe), MedDRA SOC, PT, and treatment group (Days 0 21).
- A summary by relationship (possibly, probably, definitely, or unlikely/unrelated) to test article, MedDRA SOC, PT, and treatment group (Days 0 21).

• A summary of severe related (possibly, probably, definitely) AEs, MedDRA SOC, PT, and treatment group (Days 0 - 21).

The 'twenty-one (21) days post-vaccination' dataset is intended to capture short and moderate term unsolicited AEs occurring in the approximate 3 weeks after the investigational product (or comparator) exposure and not attributable to the rescue treatment." The dataset will contain the following unsolicited AEs:

- In subjects who receive the rescue dose on Day 21, all unsolicited AEs with start dates on Days 0 to 20.
- In subjects who receive the rescue dose prior to Day 21, all unsolicited AEs with start dates on Days 0 to the day of rescue dose -1.
- In subjects who receive the rescue dose on Days 22 or 23, all unsolicited AEs with start dates on Days 0 to the day of rescue dose -1.
- In subjects who receive the rescue dose after Day 23, or who do not receive the rescue dose, all unsolicited AEs with start dates on Days 0 to 22.

In addition to the above summaries, the final analysis will also include the following summaries of unsolicited AEs:

- An overall summary of unsolicited AEs (Days 0 364).
- A summary by severity (normal, mild, moderate, or severe), MedDRA SOC, PT, treatment group (Days 0 364).
- A summary by relationship (possibly, probably, definitely, or unlikely/unrelated) to test article, MedDRA SOC, PT, treatment group (Days 0 364).
- A summary of severe related AEs, SAEs, MAEs, and SNMCs, by MedDRA SOC, PT, and treatment group will be prepared for Days 0 – 364, if any such events are reported after Day 21.

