#### 8.1.2 Unsolicited Adverse Events

Any AEs reported spontaneously by subjects will be categorized as unsolicited events and Medical Dictionary for Regulatory Activities (MedDRA) coded by system organ class (SOC)

and preferred term (PT). Solicited events with an onset after the solicitation period will also be classified as unsolicited AEs. Unsolicited events that occur within 7 days following vaccination should also be recorded in the subject diary. If any Grade 3 unsolicited event is reported during this period, subjects should be encouraged to contact the investigator by telephone. The investigator may request an *ad hoc* clinic visit at his/her judgment, and should enter any Grade 3 unsolicited adverse event reported by telephone in the unsolicited AE eCRF promptly, even if the balance of diary data is not yet available. All unsolicited AEs will be assessed for severity (as defined in Section 8.1.2) and for causality (as discussed in Section 8.5), and will be documented in the source documents and captured in the eCRF.

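### As worded, SAP 8.1.2 leaves out any adverse event that is not a diary term and starts on or after Day 7, which exposes the 21-day unsolicited AE tables

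*SAP*

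**What the plan says.** The definition in SAP 8.1.2 has two limbs. The first is "Unsolicited adverse events are defined as any adverse events occurring within the 7-day window following vaccination and not specifically solicited in the diary". The second is "or any solicited event that occurs outside the 7-day diary solicitation period". SAP 8.1.1 fixes the window by counting solicited events only if they start "within the 7-day window of the Day 0 to Day 6 post-vaccination period".

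The same section then builds its tables from the class so defined. The 21-day dataset "is intended to capture short and moderate term unsolicited AEs occurring in the approximate 3 weeks after the investigational product (or comparator) exposure". Its rules select by start date: "In subjects who receive the rescue dose on Day 21, all unsolicited AEs with start dates on Days 0 to 20"; and, where the rescue dose comes after Day 23 or is not given, "all unsolicited AEs with start dates on Days 0 to 22". For the final analysis there is also "An overall summary of unsolicited AEs" over Days 0 to 364, with matching tables by severity and by relationship.

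Protocol 8.1.2 is broader: "Any AEs reported spontaneously by subjects will be categorized as unsolicited events". There the seven days decide only whether the event should also be written in the diary. Protocol 8.1 puts all unsolicited events up to the day before the rescue dose into the 21-day profile.

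**The concern.** A non-diary event that starts on Day 7 or later satisfies neither limb. A late headache or cough, being a diary term, enters through the second limb. A late rash does not enter at all. The dataset rules do not repair this, because they filter unsolicited events by start date and do not widen the class. Late diary-type events would still fill the tables after Day 6, so a literal program would show no obvious sign that a class of events was missing.

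The 21-day all-AE profile is part of a primary safety endpoint in a first-in-human trial of this adjuvanted vaccine. SAP section 10 treats the Day 21 output as final once issued, so an error there would stand.

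**Working it through.** **Inputs.** Diary window: Days 0 to 6 (SAP 8.1.1). 21-day dataset: Day 0 to the day before the rescue dose if that dose is given by Day 23, otherwise Days 0 to 22 (SAP 8.1.2). Day 21 visit window: ± 2 days (SAP Appendix 1). One-year tables: Days 0 to 364.

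**Step 1: window lengths.** Days = last − first + 1. Diary window: 6 − 0 + 1 = 7. Dataset with rescue on Day 21: 20 − 0 + 1 = 21, which agrees with the SAP's 21-day label. One year: 364 − 0 + 1 = 365.

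**Step 2: days on which a non-diary event is ineligible under the literal wording.** Days lost = last − 7 + 1.

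| Rescue dose | Dataset | Days lost | Share |
|---|---|---|---|
| Day 19 | 0–18, 19 days | 12 | 63.2% |
| Day 21 | 0–20, 21 days | 14 | 66.7% |
| Day 23, later, or none | 0–22, 23 days | 16 | 69.6% |

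For diary-listed terms the number of days lost is zero, because the second limb admits them from Day 7.

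**Step 3: where such an event could still appear.**
- Solicited tables: no. They stop at Day 6 and hold diary terms only.
- SAP 8.2 and 8.3 outputs: only if the event is medically attended (MAE), a significant new medical condition (SNMC) or serious (SAE).
- Listings: yes. SAP 12.5 puts all eCRF data in listings.

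So a non-diary event from Day 7 that is none of MAE, SNMC or SAE reaches no AE summary table that the SAP specifies.

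**Step 4: the one-year tables.** By day count the literal wording excludes 364 − 7 + 1 = 358 of 365 days (98.1%), but that figure misleads. After Day 21 only MAEs, SAEs and SNMCs are collected, by design (Appendix 1, note 4, in both documents). SAP 8.2 and 8.3 summarise or list these to Day 364. SAP 8.2 adds that MAEs and SNMCs are in the overall AE summary, and the last bullet of SAP 8.1.2 names SAEs, MAEs and SNMCs. What remains exposed is mainly the Days 0–364 unsolicited tables by severity and by relationship.

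**Step 5: illustration, on assumed inputs.** The documents give no incidence or onset pattern for non-diary events.
- With a constant onset rate and 21-day incidence q, the tabulated incidence is 1 − (1 − q)^(7/21). For q = 20%, 30% and 40% this gives about 7%, 11% and 16%.
- SAP section 9 states a chance above 90% of seeing at least one event among 110 subjects at a true rate of 2.1%. Reproduced: 1 − (1 − 0.021)^110 = 90.3%. If only a share s of events starts in Days 0 to 6, the chance is 1 − (1 − 0.021s)^110: 82.6% for s = 0.75, 68.7% for s = 0.5 and 53.8% for s = 1/3. This applies only to events that depend on the unsolicited tables. The vaccine-related SAE that section 9 gives as an example would still be listed under SAP 8.3.

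**The case against.** The best reply is that the intended meaning is plain from the text around the sentence. The dataset is said to cover about three weeks, and its rules run to Day 20 or 22. SAP 2.2.1 and 8.1 speak of all adverse events over 21 days, and SAP section 13 declares no change from the protocol's analyses. Spontaneous reports also go to their own eCRF page (Protocol 8.1.2), so tables built by data source would have no gap. This stands as a reason to say that the loss could occur, not that it will. The documents do not specify the programming. It does not rescue the sentence, which is the only definition of the class in the SAP. Nor does the version gap explain it: the SAP cites protocol version 3.0, but the protocol's change history lists no later change to Protocol 8.1.2.

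A reader might go further and infer that the 21-day and one-year tables omit most of the follow-up. The documents do not support that. The loss concerns one class of event. All 23 diary terms stay eligible from Day 7, and the one-year classes have their own outputs (step 4).

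A reader might also fear that delayed autoimmune-type events would vanish. A hospitalised myocardial infarction is an SAE, Bell's palsy seen at an unscheduled visit is an MAE, and new rheumatoid arthritis is an SNMC. Each is reported by another route.

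**Conclusion.** The definition is wrong as written. It contradicts Protocol 8.1.2 and the SAP's stated purpose for the 21-day dataset. If it is programmed literally, non-diary events that are not serious, not medically attended and not SNMCs, with onset from Day 7 to Day 20 or 22, drop out of every AE summary table and remain only in listings. They are ineligible on 14 of 21 days with a Day 21 rescue dose, and on 63% to 70% of days for rescue from Day 19 to Day 23, later or not at all. The day counts follow from the SAP alone. The share of events lost depends on an onset pattern that the documents do not give, so the incidence and detection figures are illustrations. The one-year exposure is limited mainly to the unsolicited tables by severity and by relationship. No data are lost at collection.

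**What to change.** Replace the first sentence of SAP 8.1.2 with: *Unsolicited adverse events are (a) any adverse event that is not a diary-listed term, whatever its onset day after receipt of test article, and (b) any diary-listed event with onset after Day 6.* Leave the Day 0–20/22 dataset rules as they are, so that they alone set the time window. Make the change before the Day 21 unblinding. The cost is one sentence in the SAP, with no new data and no added analysis.

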# 3.2 Trial Endpoints

## 3.2.1 Primary Endpoints

- Number and percentage (95% confidence intervals [CI]) of subjects with solicited local and systemic adverse events over the 7 days post-injection (ie, Day 0 through Day 6 post-dosing); all adverse events (including adverse changes in clinical laboratory parameters) through 21 days post-injection; and MAEs, SAEs, and SNMCs through 1 year post-Day 0 dosing. Note: The 21 day post vaccination all adverse event profile will include all unsolicited AEs reported from test article receipt until the day preceding the rescue dose, ie, events with onset dates between days 0 to 20 for subjects who receive the rescue dose as scheduled on day 21. Rules for defining the dataset in subjects who receive the rescue dose before or after day 21, or no rescue dose, are detailed in the statistical analysis plan.
- Antibody titers specific for the HA receptor binding domains of each of the virus strains included in Tri-NIV as measured by the HAI assay at Day 0 pre-dosing and Day 21 post-dosing . Derived/calculated endpoints based on these data will include:
  - Geometric mean titer (GMT) defined as the antilog of the mean of the log-transformed HAI titers for a given treatment group.
  - $\circ$  Geometric mean ratio (GMR) defined as the ratio of post-vaccination and pre-vaccination HAI GMTs within the same treatment group (designated as GMRPost/Pre).
  - Seroconversion rate (SCR) defined as the percentage of subjects with either a baseline HAI titer < 1:10 and a post-vaccination titer  $\geq$  1:40, or a baseline HAI titer  $\geq$  1:10 and a 4-fold increase in post-vaccination HAI titer relative to baseline.
  - Seroprotection rate (SPR) defined as the percentage of subjects with an HAI titer  $\ge 1:40$ .

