# 6.1.6 Day 21 (± 2 days) – Injection 2 Visit

All subjects will return to the clinic on approximately Day 21 for the following procedures:

- Vital sign collection (heart rate, blood pressure, respiratory rate, and oral temperature).
- Review and collection of subject diary (Stage 2 subjects ONLY).
- Interval history to query for any unsolicited AEs, including MAEs, SNMCs, or SAEs, occurring since the last trial visit, and any concomitant medications taken. A directed physical examination may be performed at the investigator's discretion to evaluate any AEs.
- Blood draw for immunogenicity assessments (20 mL) and clinical safety assessments (10 mL).

- Alcohol swab cleansing of the injection site followed by IM injection into the dominant deltoid of a licensed seasonal influenza vaccine (using the manufacturer's instructions) for Group A and B subjects only, and of saline placebo for Group C subjects only. Note that if only the non-dominant deltoid is available for the injection, it is acceptable to inject the assigned trial treatment into the non-dominant deltoid. Subjects should be free of acute illness (defined as the presence of a moderate or severe illness with or without fever, or an oral temperature ≥ 38.0°C) in order to receive the second vaccination. Subjects presenting with an acute illness on Day 21 may return to the study site within the next 7 days to receive their 2nd vaccination. If a subject has experienced any AEs/SAE between study Days 0 and 21, then Day 21 vaccination may be administered or delayed for up to 7 days based on the Investigator's discretion.
- Monitoring for any AEs for 30 60 minutes following vaccination.
- Post-injection vital sign collection (heart rate, blood pressure, respiratory rate, and oral temperature) at 30 60 minutes following vaccination.
- Schedule the Day 56 visit.

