# 7.1 Clinical Laboratory Testing

The following laboratory tests will be performed by a qualified central laboratory designated by Novavax on blood samples collected from subjects on Days 0 and 21.

• Serum chemistry – alanine aminotransferase (ALT), aspartate aminotransferase (AST), total bilirubin, alkaline phosphatase (ALP), creatinine, and blood urea nitrogen (BUN).

Hematology – complete blood count (CBC) with hemoglobin, hematocrit, red blood cell (RBC) count, platelet count, and white blood cell (WBC) count with differential.

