2.2 Study Endpoints

2.2.1 Primary Endpoints

• Number and percentage (95% confidence interval [CI]) of subjects with solicited local and systemic adverse events over the 7 days post-injection (ie, Day 0 through Day 6 post-dosing); all adverse events (including adverse changes in clinical laboratory parameters) through 21 days post-injection; and MAEs, SAEs, and SNMCs through 1 year post-Day 0 dosing.

- Antibody titers specific for the HA receptor binding domains of each of the virus strains included in Tri-NIV as measured by the HAI assay. Derived/calculated endpoints based on these data will include:
 - Geometric mean titer (GMT) defined as the antilog of the mean of the log-transformed HAI titers for a given treatment group.
 - \circ Geometric mean ratio (GMR) defined as the ratio of post-vaccination and pre-vaccination HAI GMTs within the same treatment group (designated as GMR_{Post/Pre}).
 - Seroconversion rate (SCR) defined as the percentage of subjects with either a baseline HAI titer < 1:10 and a post-vaccination titer ≥ 1:40, or a baseline HAI titer ≥ 1:10 and a 4-fold increase in post-vaccination HAI titer relative to baseline.
 - Seroconversion rate difference defined as the difference of seroconversion rates between each of the Tri-NIV vaccine groups and Fluzone HD group and its upper 95% CI.
 - Seroprotection rate (SPR) defined as the percentage of subjects with an HAI titer \ge 1:40.

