8.1 Analyses of Primary Objectives of Safety

Safety will be assessed in the Safety population including all subjects who receive any test article, and will be summarized overall and by treatment group based on solicited local and systemic adverse events, 21-day all AE profile (including adverse changes in clinical laboratory parameters) by Medical Dictionary for Regulatory Activities (MedDRA) preferred term, severe, related (possibly, probably, or definitely), and one-year MAEs, SAEs and SNMCs profiles. The number and percentage (95% CI) of subjects in each treatment group with a given term will be summarized. A listing and narratives of SAEs will also be produced.

Solicited adverse events occurring in the first 7 days after each dose of test article will be presumed to be related; and severity will be graded by specific definitions included in the protocol and subject diary. Unsolicited adverse event summaries by relationship to test article will be categorized as "not related" (including "unrelated" or "unlikely") or "related" (including "possible", "probable", and "definite"). For multiple occurrences of an adverse event in the same subject, a subject will be counted only once, using the most severe or most related occurrence for the summarization by severity or relationship to test article, respectively.

Solicited adverse events will not be coded, and will be summarized by solicited term only. All unsolicited adverse events will be coded using MedDRA version 20.0.

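### The 21-day AE dataset ends the day before the second injection, so laboratory AEs from a safety sample drawn that same day miss the primary 21-day tables

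*SAP*

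**What the plan says.** SAP 2.2.1 sets the primary safety endpoint as "all adverse events (including adverse changes in clinical laboratory parameters) through 21 days post-injection", alongside solicited events and the one-year events. Protocol 3.2.1 has the same endpoint. SAP 8.1 says how it will be reported: "21-day all AE profile (including adverse changes in clinical laboratory parameters) by Medical Dictionary for Regulatory Activities (MedDRA) preferred term, severe, related".

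Protocol 7.1 has the safety laboratory tests "performed by a qualified central laboratory designated by Novavax on blood samples collected from subjects on Days 0 and 21". Day 0 is baseline, so the Day 21 (±2) visit gives the only scheduled post-dose values. Protocol 6.1.6 lists the draw ("Blood draw for immunogenicity assessments (20 mL) and clinical safety assessments (10 mL") ahead of the second injection at that visit. Under Protocol 8.1.4, a rise in toxicity grade over baseline that reaches at least Grade 2 is reported as an AE.

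The note in Protocol 3.2.1 runs the 21-day profile "until the day preceding the rescue dose, ie, events with onset dates between days 0 to 20" for subjects injected on schedule. SAP 8.1.2 has the matching rule: "In subjects who receive the rescue dose on Day 21, all unsolicited AEs with start dates on Days 0 to 20". For injections before Day 21, or on Day 22 or 23, the dataset also ends the day before. For later injections or none, it ends on Day 22. The same section labels its 21-day tables as Days 0 to 21, and says the dataset is meant to leave out events attributable to the rescue treatment.

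**The concern.** The endpoint names laboratory changes as part of the 21-day AE profile, but the window closes before the visit that supplies them. The cut-off is disclosed and deliberate; its effect on laboratory AEs is not addressed. It also goes beyond its stated purpose, because a sample taken before the injection cannot show an effect of that injection.

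At stake are the laboratory entries in the first report's AE tables: counts by preferred term, by severity and by the investigator's view of relationship. This is a first-in-human trial with safety as a primary objective. SAP Section 10 treats the Day 21 analyses as final and not open to later revision.

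The rule also depends on the term rescue dose. The Day 21 column heading of Protocol Table 1 applies it to all three groups. Note 2 to that table and note 6 to Appendix 1 use it for Tri-NIV recipients and call the Group C injection placebo. On that narrower reading Group C never receives a rescue dose and its dataset runs to Day 22.

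**Working it through.** **The plan's own planning figures (Protocol 10.5, SAP 9).** The chance of seeing at least one event is 1 − (1 − p)^n.
- n = 110, p = 2.1%: 90.3%. n = 220, p = 1.1%: 91.2%. The plan states above 90% for both.
- Upper one-sided 95% bound with no events, 1 − 0.05^(1/n): 2.69% and 1.35%. The plan states 2.7% and 1.4%.

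These reproduce, but they presume that events enter the dataset.

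**Inputs.** Draw day d = 19 to 23 (Day 21 ±2). Second injection on day r: the same day, 1 to 7 days later (Protocol 6.1.6), or not given. Dataset end E = r − 1 if r ≤ 23, otherwise 22 (SAP 8.1.2). The documents give no start-date rule for laboratory AEs, so I take the sample date first and then a later result date.

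**Same-day draw and injection (r = d).**

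| Visit day d | 19 | 20 | 21 | 22 | 23 |
|---|---|---|---|---|---|
| Dataset end E = d − 1 | 18 | 19 | 20 | 21 | 22 |
| Sample-dated AE kept | no | no | no | no | no |

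Kept: 0 of 5. A start date 1 to 7 days later, when the result is known, falls further past E: again 0 of 5 at each lag.

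**Injection delayed by k = 1 to 7 days, sample at the original visit.** If d + k ≤ 23, then E = d + k − 1 ≥ d and the AE is kept. If d + k > 23, then E = 22, so it is kept for d = 19 to 22 and lost for d = 23. Kept: 4 of 5 draw days at every k.

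**Injection not given (E = 22).** Sample-dated: 4 of 5. Dated 1, 2 or 3 days later: 3, 2 or 1 of 5. The start-date rule therefore matters here.

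**Group C under the narrow reading of rescue dose (E = 22).** A sample-dated AE is kept on 4 of 5 draw days, against 0 of 5 for Groups A and B with same-day injection.

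**Effect on the planning probability.** Assume a share s of subjects has a delayed or missed injection and a draw on Days 19–22; the documents give no such share. With n = 110 and p = 2.1%, the chance that the table shows at least one laboratory AE is 1 − (1 − 0.021s)^110: 0% for s = 0, 10.9% for s = 5%, 20.6% for s = 10%, instead of 90.3%.

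**Illustrative counts.** The laboratory-AE rate and same-day share are assumptions. With 110 subjects and rates of 2%, 5% and 10%, the expected numbers are 2.2, 5.5 and 11.0. With 80–100% injected on the draw day, 1.76–2.2, 4.4–5.5 or 8.8–11.0 subjects per affected group would be absent from these tables.

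**The case against.** **The data are reported elsewhere.** This stands in large part. Laboratory values are tabulated by toxicity grade (Protocol 8.1.4), with grade changes from baseline at Day 21 (Protocol 10.4.1.1). Recorded data go into listings (SAP 12.5), and the final analysis has Days 0–364 AE tables. A reader might infer that laboratory safety data are lost; they are not. Grade tables, however, give no counts by preferred term or relationship, and the Days 0–364 tables come only at the end. SAP 12.5 does not say whether listings accompany the abbreviated Day 21 report. The Day 0–21 summary of medically-attended events would not normally pick up an asymptomatic shift, since SAP 8.2 ties those to a visit for symptomatic illness or injury.

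**The tables are labelled Days 0–21, so a sample dated Days 19–21 may belong in them.** The label conflicts with the dataset rule in the same section. The detailed rule probably governs, but the text should not leave that open.

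**Laboratory AEs may not be unsolicited AEs.** Protocol 8.1.2 says "Any AEs reported spontaneously by subjects will be categorized as unsolicited events". SAP 8.1.2 covers "any adverse events occurring within the 7-day window following vaccination and not specifically solicited in the diary", plus solicited terms outside the diary period. If laboratory AEs are neither, the cut-off does not reach them, and the gap is a table promised in SAP 8.1 that no list of outputs contains. The SAP definition read literally would also omit ordinary non-solicited AEs after the first week, so it is weak evidence about laboratory AEs in particular.

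**Other readings that go too far.** A reader might infer a bias between arms. That is not established: it would need the narrow reading of rescue dose, which Table 1's heading contradicts. Nor can it be said that the window is the same in every arm, since the notes support the narrow reading. A reader might also infer that a delayed injection moves the sample with it and loses the AE again. Appendix 3 fixes the draw at Day 21 (±2), and Protocol 6.1.6 has ill subjects return for the injection. Finally, the loss is not total: early-termination draws before the cut-off would normally stay in.

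**Conclusion.** The concern holds on the planned pathway. With draw and injection on the same day, a laboratory AE from the Day 21-visit sample is kept on 0 of 5 visit days, so the laboratory part of the primary 21-day AE tables will be nearly empty. With a delayed or missed injection and the sample at its original visit, 4 of 5 draw days are kept and Day 23 is lost. The 4 of 5 assumes dating to the sample; the 0 of 5 holds for sample or later dating.

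The exclusion does not depend on whether blood is drawn before the injection. The case for putting these AEs back does, and that order is only inferred: Protocol 6.1.6 lists the draw first, but Appendix 3 labels only the Day 0 draw as pre-vaccination.

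Whether all groups are affected alike depends on what rescue dose means, which the documents leave unsettled. The consequence is a gap in the Day 21 report of a descriptive trial. It is worth correcting before those tables are fixed.

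**What to change.** In SAP 8.1.2:

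1. Date a laboratory AE to the collection date of its sample.
2. Include in the 21-day dataset any AE from the scheduled Day 21-visit safety sample collected within Days 19–23 and before any second injection, whether or not the subject reported it spontaneously. Capture then becomes 5 of 5 draw days for same-day, delayed and missed injections.
3. Keep the day-before cut-off for all other AEs, including vital-sign AEs, because vital signs are taken both before and after the injection (Protocol Appendix 1, note 1). For this rule only, define rescue dose as the second injection in every group, including the Group C placebo, so that the window is the same in all arms.
4. Align the Days 0–21 table labels with the dataset rule and confirm that the draw precedes the injection. Make the matching change to the protocol note, or record it in SAP Section 13, which lists no changes.

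The cost is one derivation rule, a link from each laboratory AE to its sample, and the note or Section 13 entry. If the draw order cannot be confirmed for all subjects, draw and injection times are needed as well. No visit, sample or treatment changes.
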